2.15 AUDITS AND INSPECTIONS

The trial may be subject to audit by the London School of Hygiene & Tropical Medicine under their remit as Sponsor, the Study Coordination Centre and other regulatory bodies to ensure adherence to GCP.

2.16 END OF TRIAL FOR PARTICIPANTS

The follow-up period ends 15 months after the first treatment day with a final contact (telephone or face-to-face) with the Research Nurse as described above. This will be considered as the end of trial for patients.

2.17 ANALYSIS

Individual N-of-1 trials: The purpose of these analyses is to inform the individual patient of the effect of the IMP on their VAS muscle symptom score. The analysis and presentation of individual level results will be developed in collaboration with the Patient and Public Involvement (PPI) group. We will examine a range of graphical summaries and statistical analyses in order to identify the most informative presentation of individual results. As a result of this process, at the end of each individual trial the participant will be shown numerical and graphical summaries of their individual data, in relation to their IMP and placebo periods.

Combined analysis of N-of-1 trials

Primary analysis: To estimate the population average estimate of the trial treatment n VAS muscle symptom score, data from each N-of-1 trial will be aggregated to form a powerful dataset. We will adopt an intention-to-treat approach. Patients who enter data on muscle symptoms at least once during a treatment period with the IMP and at least once during a treatment period with placebo will be included in the primary analysis.

The primary analysis will be a linear mixed model for VAS muscle symptom score with random effects for participant and treatment and fixed period effects. Residual errors will be modelled using

a first-order auto-regressive error structure within each treatment period to account for correlation between the 7 daily measurements, with robust standard errors to account for non-normality of the VAS scores. Although VAS muscle symptom scores are unlikely to be exactly normally distributed, analysing such data using normal-based methods is likely to be a sufficiently robust approach.²⁶ All tests will be two-sided. $p < 0.05$ will be considered statistically significant.

Secondary analyses: Secondary outcomes relating to the impact of the IMP on other aspects of life will be analysed in a similar manner to the primary outcome, omitting the auto-regressive correlation structure since these secondary outcomes are measured once per treatment period. We will investigate whether the excess muscle symptoms, if any, experienced during treatment periods with the IMP appears to be concentrated in multiple sites.

Descriptive statistics will be used to summarise the measures of adherence to randomised treatment, and their relationship to the IMP and placebo periods. We will use the measures of adherence to randomised treatment to perform an efficacy analysis based around an instrumental variables approach.²⁷ Because these analyses require much stronger assumptions than the intention-to-treat analysis above, the results of the efficacy analysis will be presented and interpreted as a secondary analysis. The secondary outcomes include a single binary measure of whether the participant reports having muscle symptoms during that treatment period or not. This will be combined with the follow-up question pertaining to attribution, to obtain a single binary measure of whether the participant reports having muscle symptoms that they attribute to the study medication or not. These two binary outcome measures will be assessed using a logistic mixed model with random participant and treatment effects and fixed period effects.

We will relate the patients' decision regarding future statin use, and whether or not the participant found their own result helpful in making their subsequent treatment decisions, to their individual estimated effect of the IMP.

Subgroup analyses: There are no priori subgroup analyses planned. If an overall population-level effect is detected, we may investigate whether the effect varies within subgroups defined by measured baseline characteristics. These analyses will be regarded and interpreted as being exploratory.

3. Trial Organisation and Responsibilities

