2.10.4 PATIENTS REPORTING INTOLERABLE SYMPTOMS

The GP will remain as the first point of contact for patients during the trial for their care. Intolerable muscle symptoms should be reported to the GP who will provide clinical care as directed by the appropriate NICE guidelines. Where a patient reports intolerable symptoms, Figure 2 shows the decision making pathway for the GP and the patient.

For patients who experienced intolerable muscle symptoms, and who do not want to be withdrawn early from the trial, the GP will be asked to confirm that the patient still meets the trial eligibility criteria. Patients who continue to meet the eligibility criteria can be offered the following options by the GP, depending on their clinical judgement:

- i. continue with their current treatment
- ii. reduce the frequency of tablet use to every other day rather than daily
- iii. stop for that treatment period and resume at the start of the next period

[figure not shown]

Figure 2: Intolerable symptoms pathway

Patients who withdraw from treatment temporarily or permanently will be asked to inform the study team and report symptoms at the time of stopping, and continue to submit outcome data for their current treatment period.

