1.10 ANALYSIS PRINCIPLES FOR FINAL ANALYSIS

- All analyses will be conducted on an ‘intention-to-treat’ basis, defined as follows:
 - All patients who enter at least one VAS score for muscle symptoms during a statin period and at least one VAS score for muscle symptoms during a placebo period will be included in the final primary analysis.
 - For analyses of secondary outcomes from the patient questionnaire (single monthly measurement), analyses will include all patients who complete at least one measure during a statin period and at least one measure during a placebo period.
 - Periods of allocation to statin will be compared to periods of allocation to placebo, irrespective of adherence to the allocated treatment.
- All statistical tests will be two-sided, and the nominal level of α will be 5%. Confidence intervals for the primary outcome will be set at the 95% level.
- P values will not be adjusted for multiplicity. However, the outcomes are clearly categorised by degree of importance (primary and secondary). Confidence intervals for secondary outcomes will be set at the 99% level.
- The primary analysis will not impute missing values. Where the number of missing observations is substantial, we will report the number of observations used in the analysis. Robustness of conclusions to missing data will be explored via sensitivity analysis.
- Analyses exploring the effect of adherence on primary and secondary outcomes will be undertaken as secondary analyses.
- All adverse events will be coded using MedDRA Version 19.1.

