2.3.4 SENSITIVITY ANALYSES

The sensitivity analyses planned were chosen in line with the view that sensitivity analyses should address exactly the same question as the main analyses but be valid under different (potentially verifiable) assumptions, and that if the results are qualitatively different to those in the main analysis, there would be genuine doubt as to which are the correct results. If this does occur, both the main analyses and the results of the sensitivity analyses will be reported in a transparent manner.

Correlation structure

We will explore the robustness of conclusions to different assumptions about the correlation structure of residual errors between the primary outcome measures from the same participant within the same week.

Fixed treatment effect

We will compare the main analyses with random treatment effects to models with a fixed treatment effect only.

Period and carry-over effects

We will add fixed period effects to the primary and secondary outcome models. Because participants will start their individual N-of-1 trials at different times of the year, there is no reason to expect there to be a period effect. We will not explore carry-over effects; the trial was designed to avoid such effects.

Missing data

The mixed model described above is valid under outcome data being missing at random given the observed outcome data. We will use multiple imputation to perform an analysis valid under missing at random given both the observed outcome data and the measured baseline characteristics. We will then consider a number of simple scenario analyses to assess the robustness of our findings to outcome data being missing not at random.

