2.3.7 SECONDARY ANALYSES

Withdrawal, Loss to follow-up and Adherence – Descriptive analyses

Loss to follow up and withdrawal, with reasons for withdrawal, will be summarized by overall frequencies and percentages. Protocol violations will be tabulated. Descriptive statistics, including graphical summaries, will be used to summarise the measures of adherence to randomized treatment and withdrawal, and their relationship to the statin and placebo periods.

Withdrawal – Comparison between statin and placebo periods

We will explore whether the period in which a patient was first known to have withdrawn was more likely to have been a placebo or a statin period. If this date is after the end of a treatment period but the patient chooses not to begin the next period, the period in which the withdrawal happens will be set to the period just ended.

Adherence – Randomised comparison

We will explore whether adherence was lower on statin periods compared with placebo periods using mixed models similar to those described above.

Adherence – Efficacy analyses

We will use the measures of adherence to randomised treatment to perform an efficacy analysis based around an instrumental variables approach. Because these analyses require much stronger assumptions than the intention-to-treat analysis above, the results of the efficacy analysis will be presented and interpreted as a secondary analysis.

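### The both-treatments entry rule drops Period 1 scores already collected, so the SAP's missing-at-random claim does not cover the primary analysis set; the resulting bias is conditional and usually modest

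*Protocol*

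**What the plan says.** Protocol 2.17 limits the primary analysis to "Patients who enter data on muscle symptoms at least once during a treatment period with the IMP and at least once during a treatment" (meaning on placebo). SAP 1.10 has the same rule: "All patients who enter at least one VAS score for muscle symptoms during a statin period and at least one VAS score for muscle symptoms" (the latter on placebo). The SAP lists it under the statement "All analyses will be conducted on an ‘intention-to-treat’ basis, defined as follows". The protocol synopsis and SAP 1.1 repeat the rule as the criterion for evaluation.

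Protocol 2.8 gives eight sequences, all with opposite treatments in Periods 1 and 2. Protocol 2.10.4 asks patients who stop treatment, for a time or for good, to report their symptoms when they stop and to "continue to submit outcome data for their current treatment period".

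On missing data, SAP 1.10 says "The primary analysis will not impute missing values", and SAP 2.3.4 says "The mixed model described above is valid under outcome data being missing at random given the observed outcome data". SAP 2.3.4 adds multiple imputation using baseline characteristics and "simple scenario analyses to assess the robustness of our findings to outcome data being missing not at random". It does not say which patients enter either analysis.

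SAP 2.3.7 says "Loss to follow up and withdrawal, with reasons for withdrawal, will be summarized by overall frequencies and percentages". The same section also plans to describe withdrawal in relation to statin and placebo periods, and to examine whether first withdrawal fell more often in a statin or a placebo period.

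**The concern.** The trial enrols people who stopped a statin, or were considering it, because of muscle symptoms. Protocol 2.4 allows for 40% loss to follow-up, and intolerable muscle symptoms are a listed reason for withdrawal (End of Trial form, B.3.b). Some patients may complete the Period 1 daily scores, find them bad and leave. The entry rule then removes those scores.

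A likelihood-based mixed model handles dropout that depends on observed scores because those scores stay in the likelihood. If the score that explains the dropout is deleted together with the patient, the remaining set is a selected sample and that justification lapses. Such a set is also not intention-to-treat in the usual sense, since entry depends on what happened after randomisation. At stake is whether the headline estimate refers to everyone randomised who gave data, or to those who stayed long enough to try both treatments.

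**Working it through.** **The plan's own figures.** Three statin and three placebo periods give a per-patient contrast with variance σ²(1/3 + 1/3). With the within-patient SD of 30 from the rationale in Protocol 2.3, two-sided 5% and 90% power:

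- n = (1.960 + 1.282)² × 900 × (2/3) / 10² = 63.04, rounded up to 64; power at 64 is 90.4%.
- 64 / (1 − 0.40) = 107, and 107 × 1.8 = 193, in line with the final 200.

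The simulation description in Protocol 2.3 uses a residual SD of 25, which would give n = 44. The two sets of SDs should be reconciled, but that is a separate matter. Below I use between-patient SD 35 and within-patient SD 30. The sample size is not affected by the present point.

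**Why the rule can bias.** Write the Period 1 score as y = μ + u + T·d + e, where T is 1 on statin, d is the patient's own statin effect (mean 10, SD τ, independent of u), and e has SD σ = 30. Suppose loss occurs only after Period 1, with probability a + b·y. Let s_S and s_P be the proportions staying among statin-first and placebo-first patients. Among stayers, the mean of any component X shifts by −b·cov(X, y)/s. So:

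- statin-first contrast: shift −bτ²/s_S − bσ²/(3s_S)
- placebo-first contrast: shift +bσ²/(3s_P)

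Weighting by s_S and s_P, the σ² terms cancel and the bias is **−bτ² / (s_S + s_P)**.

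Assumed inputs, for which the documents give no figures: μ = 30, a = 0.1, b = 0.003 per mm. Then s_S = 1 − 0.1 − 0.003 × 40 = 0.78 and s_P = 1 − 0.1 − 0.003 × 30 = 0.81.

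- τ = 0: bias 0.
- τ = 15: −0.003 × 225 / 1.59 = −0.42, so 10 becomes 9.58.
- τ = 25: −0.003 × 625 / 1.59 = −1.18, so 10 becomes 8.82.
- True mean 0, τ = 15: −0.003 × 225 / 1.62 = −0.42, slightly below zero.

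The bias vanishes if b = 0 (leaving unrelated to the score) or τ = 0 (common effect), and changes sign if low scorers leave (b < 0).

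**Simulation.** 200,000 patients per scenario, period-level normal scores without bounds, eight sequences, maximum likelihood with random participant and treatment effects, and no autoregressive errors. Leaving depends only on the score just recorded. True mean effect 10 mm.

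| Leaving | Effect SD | Excluded, statin-first / placebo-first | All data | Both-treatments rule |
|---|---|---|---|---|
| After Period 1, linear as above | 0 | 22% / 20% | 9.93 | 9.94 |
| same | 15 | 23% / 20% | 10.06 | 9.64 |
| same | 25 | 23% / 20% | 9.98 | 8.88 |
| Any period, scores over 80 | 0 | 12% / 8% | 10.03 | 9.90 |
| same | 15 | 12% / 8% | 9.94 | 9.42 |
| Any period, steep in score | 0 | 21% / 17% | 10.05 | 9.88 |
| same | 15 | 22% / 17% | 10.04 | 9.21 |
| Any period, low scorers leave | 15 | 16% / 19% | 9.97 | 10.35 |
| Extreme: after Period 1, about 41% lost | 15 | 44% / 37% | 9.93 | 8.61 |
| same | 25 | 44% / 37% | 9.99 | 6.66 |

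With true mean zero, high scorers leaving and a varying effect, the rule gave −0.3 to −1.2 mm at effect SD 15, and −2.6 to −3.0 mm in the extreme cases at SD 25.

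Standard errors at N = 200 barely differ: 2.26 (all data) vs 2.29 (rule) in the second row, 2.45 vs 2.45 in the steep scenario at SD 15, and 3.06 vs 3.14 in the last row.

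**A different effect distribution.** With SDs 30 and 25, 40% leaving, and a minority of strong reactors in place of a normal spread: 30% reacting by 33 mm gave 9.0 under the rule against 9.7 with all data; 20% reacting by 50 mm gave 7.8–7.9 against 9.0–9.1. Here all data also falls short of 10, probably because a normal random effect does not describe two groups. A further set of runs (100,000 patients per scenario, 31–39% dropout, symptom-driven leaving, varying effects) gave 8.1–9.8 under the rule against 9.1–10.2.

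**The case against.** **Timing.** This is the strongest argument. Daily scores are collected only in the last week of each period. A patient who reacts in week 2 and leaves the study has no daily score and is lost under any rule. One who stops capsules early but keeps reporting gives an off-drug score in week 8, since the product information (Appendix 8, 5.2) puts the half-life at about 14 hours. When every leaver submits off-drug scores, the rule and all data give 6.1 vs 6.3 mm (20% reacting by 50 mm) and 7.7 vs 7.8 mm (30% by 33 mm). This stands: the fix helps only with patients who score on treatment and then leave.

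**Existing safeguards.** A reader of the sentence on overall frequencies might infer that withdrawal is never examined by treatment. SAP 2.3.7 does examine it; only the split by reason is missing. Nor can one infer that imputation and the not-at-random scenarios leave these patients out, because the SAP is silent. But none of these analyses is stated to correct the primary estimate.

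**Retention.** Protocol 2.10.4 gives patients with intolerable symptoms ways to stay in the trial, and non-adherent periods are analysed as allocated. The documents give no figure for leaving in Period 1. The idea that the typical excluded patient is a statin-first reactor is not supported: in the simulations, statin-first exclusions were only a few percentage points higher.

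**Prespecification.** The rule is stated openly in both documents, so the intention-to-treat label is the lesser issue. The missing-at-random sentence is the one that needs repair.

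**Conclusion.** The point holds as a conditional one. The rule discards collected Period 1 scores, selects on response after randomisation, and takes the primary set outside the justification in SAP 2.3.4 when leaving depends on the Period 1 score. For a true 10 mm effect, with high scorers leaving after scoring and effects varying between patients, the estimate is roughly 0.4 to 1 mm lower than with all data in moderate scenarios. At effect SD 15 that is about 0.2 to 0.3 of a standard error (0.42/2.26 to 0.83/2.45). Figures such as 6.7 mm need effect SD 25 and the whole 40% loss concentrated after Period 1.

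Two stronger readings should be resisted. One is that the rule biases the statin effect toward zero as a matter of fact. The gap is at most about 0.2 mm with a common effect, nil if leaving is unrelated to symptoms, and in the other direction if low scorers leave. The documents fix neither the dropout mechanism nor the effect SD. The other is that the rule is harmless when statins have no average effect. That is true only if the effect does not vary; otherwise the estimate moves below zero and falsely favours statin. Protocol 2.4 considers variation in individual effects, and SAP 2.3.1 models it.

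The sizes rest on assumed dropout functions, a mean score of 30, unbounded normal scores and independence of a patient's level and effect.

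**What to change.** - **Protocol 2.17 and SAP 1.10:** fit the same primary mixed model to every randomised patient with at least one daily VAS score in any period. Keep the both-treatments set as a sensitivity analysis. Align the evaluation criterion in the protocol synopsis and SAP 1.1.
- **SAP 2.3.4:** state that multiple imputation and the not-at-random scenarios include the patients with data on one treatment only.
- **SAP 2.3.7:** to the planned comparison of the period of first withdrawal, add the split by reason (intolerable muscle symptoms, form B.3.b), and report exclusions from the both-treatments set by first-period treatment.

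The cost is wording: same model, same data, and SAP section 1 leaves the plan open until database lock. One-treatment patients bring in a little between-patient information, whereas SAP 2.3.6 justifies the absence of adjustment by within-patient comparison; that sentence needs a qualifier. The standard error hardly changes. In the scenarios run, using all data never did worse than the rule beyond simulation noise.

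A separate Period 1 comparison of statin-first with placebo-first patients is not needed. At 100 vs 100 it has about 44% power for 10 mm with SDs 30 and 25, and about 34% with SDs 35 and 30.

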3.1 SPONSORSHIP AND TRIAL MANAGEMENT

The StatinWISE trial is sponsored by the LSHTM and its responsibilities coordinated by the CTU. The CTU may delegate responsibilities to third parties which will be outlined in relevant agreements. The responsibilities of the CTU will be overseen by the Trial Management Group (TMG).

3.2 INDEMNITY

LSHTM accepts responsibility attached to its sponsorship of the trial and, as such, would be responsible for claims for any non-negligent harm suffered by anyone as a result of participating in this trial. The indemnity is renewed on an annual basis and LSHTM assures that it will continue renewal of the indemnity for the duration of this trial.

The DMC has the responsibility for deciding whether, while randomisation is in progress, the unblinded results (or the unblinded results for a particular subgroup), should be revealed to the TSC. The DMC Charter states that they will do this if, and only if, the following two conditions are satisfied: (1) the results provide proof beyond reasonable doubt that treatment is on balance either definitely harmful or definitely favorable for all, or for a particular category of participants in terms of the major outcome; and (2) the results, if revealed, would be expected to substantially change the prescribing patterns of clinicians who are already familiar with any other trial results that exist. Exact criteria for “proof beyond reasonable doubt” are not, and cannot be, specified by a purely mathematical stopping rule, but they are strongly influenced by such rules. The DMC Charter is in agreement with the Peto-Haybittle stopping rule whereby an interim analysis of a major endpoint would generally need to involve a difference between treatment and control of at least three standard errors to justify premature disclosure (Haybittle 1971; Peto 1977). An interim subgroup analysis would, of course, have to be even more extreme to justify disclosure. This rule has the advantage that the exact number and timing of interim analyses need not be pre-specified. In

summary, the stopping rules require extreme differences to justify premature disclosure and involve an appropriate combination of mathematical stopping rules and scientific judgment.

3.6 PRINCIPAL INVESTIGATOR'S' RESPONSIBILITIES

Coordination within each participating general practice will be through a local PI whose responsibility will be detailed in an agreement in advance of starting the trial and will include:

- ensure all necessary regulatory approvals are in place prior to starting the trial
- delegate trial related responsibilities only to suitably trained and qualified personnel
- train relevant medical and nursing staff who see patients and ensure that they remain aware of the state of the current knowledge, the trial and its procedures (there are wall charts, pocket summaries and PowerPoint presentations to assist with this)
- agree to comply with the final trial Protocol and any relevant amendments
- ensure that all patients who meet the eligibility criteria are considered promptly for the trial
- ensure consent is obtained in line with local approved procedures
- ensure that the patient baseline data are completed and transmitted to the CTU in a timely manner
- ensure the Investigator's Study File is up-to-date and complete
- ensure all adverse events are reported promptly to the CTU
- ensure the trial is conducted in accordance with ICH GCP and fulfils all national and local regulatory requirements
- allow access to source data for monitoring, audit and inspection
- be responsible for archiving all original trial documents including data forms for five years after the end of the trial

